7.2.2 Treatment Period

The following assessments and procedures should be performed during the Treatment Period. Not all of the assessments and procedures listed below are to be performed at every scheduled visit (e.g., selected assessments are performed at Weeks 4 and 8). For the timing of when to administer individual assessments and procedures, see the Schedule of Assessments in [Table 1, Section 7.1](#). Unless otherwise indicated, assessments should be performed before the first ECP treatment of the week.

Corticosteroid Dose Record

The patient's steroid dosing for the treatment of aGvHD must be documented on the Corticosteroid Dosage Form of the eCRF. Dosages should be recorded without modification (although average daily dose is acceptable). Methylprednisolone equivalence will be calculated later.

Physical Examination

A qualified health-care professional will give each patient a complete physical examination to document any changes in the general health of the patient by organ system. The complete physical examinations will be performed after all other assessments included in Weeks 4, 8, 12 and 16 have been completed. Targeted physical examinations will be performed after all other assessments included in Weeks 1, 2, 3, 5, 6, 7, 9, 10, and 11 have been completed. Patient height and weight will also be recorded each week. In those weeks when patients are reporting to the study site multiple times, height and body weight need only be recorded at the first visit.

A new calculation of Total Blood Volume is necessary before each treatment to estimate the safe extracorporeal blood volume that may be allowed for the patient undergoing treatment. These calculations should be performed using the current weight (recorded at the first visit of the week) and current hematocrit (drawn after the last photopheresis treatment and within 48 hours before the next photopheresis treatment).

Pregnancy Test

A urine dipstick pregnancy test will be performed at screening and weekly for all females of childbearing potential (defined as those who have reached the onset of menarche or 8 years of age, whichever comes first) on the day of the first scheduled treatment of the week, before the start of the day's therapy. A serum test may also be performed in place of a urine dipstick. If the urine dipstick result is positive, blood must be drawn for a serum HCG level and analyzed locally before any ECP treatment. A positive serum HCG result necessitates automatic withdrawal of the patient from active treatment, and no further ECP treatments can be performed.

Vital Signs

Vital signs (diastolic and systolic blood pressures, pulse rate, respiratory rate, and temperature) will be taken before and at the end of each ECP treatment.

Lansky Performance Status

A qualified health-care professional (physician, physician's assistant, nurse practitioner) will evaluate the patient's Health Performance Status using the Lansky Performance Status Scale ([Appendix C: Lansky Scale](#)) after 4, 8 and 12 weeks of ECP treatment.

Local Laboratory Analyses

Laboratory assessments (including pregnancy tests) will be performed through a local laboratory. The data obtained should be entered into the eCRF.

Clinically significant laboratory abnormalities should be recorded as AEs according to the Principal Investigator's judgment. Blood samples may be obtained through standard venipuncture technique or through a venous access catheter, according to institutional guidelines.

During the Treatment Period, blood will be collected at the indicated times and processed for the following:

Before the First Scheduled ECP Treatment of the Study at Week 1

- Total bilirubin, to be used for the baseline aGvHD status assessment.

Before Each Scheduled ECP Treatment (Weeks 1-12)

- Hematocrit, as indicated in the CELLEX System Operator's Manual.
- Platelets, as clinically indicated.
- WBC count, as clinically indicated.
- Ionized calcium, as clinically indicated and/or according to institutional guidelines (particularly for patients whose ECP treatments include the use of ACD-A as an anticoagulant).
- Total bilirubin, to be used for the prior weekly assessment of aGvHD status
 - Levels drawn before the first ECP treatment of Week 5 and Week 9 should be used for the Primary and Secondary Endpoint aGvHD status assessments, respectively. On Days 28 and 56, the bilirubin assessments must be done within ± 2 days.

Monthly Before the First ECP Treatment of the Week at Weeks 5 and 9

- CBC with differential (WBC, platelets, hemoglobin, hematocrit, neutrophils, lymphocytes, basophils, eosinophils, and monocytes) and an absolute neutrophil count.
- Electrolyte panel (sodium, potassium, chloride, bicarbonate, BUN, creatinine, and

glucose), BUN/creatinine ratio, calcium, phosphorous, and magnesium.

- AST, ALT, GGT, total bilirubin, direct bilirubin, indirect bilirubin, alkaline phosphatase, and lactate dehydrogenase.

During ECP Treatments (Weeks 1-12)

- Laboratory analyses needed to assess patients should be drawn at the discretion of the Principle Investigator.

At Screening and Weekly (Weeks 1-12) for All Females of Childbearing Potential

- Urine dipstick pregnancy testing (for females age 8 or those who have reached the onset of menarche, whichever comes first). A serum test may also be performed in place of a urine dipstick.
- Serum HCG level immediately after any positive urine pregnancy test.

Any laboratory test results that are needed to manage aGvHD or other medical conditions should be drawn outside this schedule as clinically indicated.

Assessment of aGvHD Status

All patients will be evaluated for a response in their aGvHD manifestations at least once each week through Week 12 (or the visit at which the patient ceases to receive treatment, if before Week 12). The assessment of aGvHD status should occur after the last ECP treatment of the week, with the exception of bilirubin levels, which will be tested prior to the first ECP treatment of the following week.

Patients will be evaluated by the treating physician for the presence or absence of aGvHD manifestations of the skin, liver, and gut. Source data will be collected for each patient and entered into the eCRF, and a scoring algorithm will be applied to calculate the grade of aGvHD using the modified IBMTR Severity Index and the modified Glucksberg criteria. Acute GvHD status will be assessed at baseline (at Week 1 before the first ECP treatment of the study) and once a week, after the last ECP treatment of each week (Weeks 1-12).

Skin aGvHD Staging

Only active rash (erythema) is considered in body surface area (BSA) calculations. Hyper- (e.g., brown/tanned rash) or hypopigmentation representing post-inflammatory changes are not included in the BSA assessment. Skin involvement will be reported as % BSA using the Rule of Nines ([Appendix G: Percent Body Surface Area Assessment](#)) and/or presence of bullae.

Other common etiologies for skin symptoms include drug rash, conditioning regimen toxicity, infection, and cytokine storm/engraftment syndrome.

Liver aGvHD Staging

Bilirubin will be determined from a single blood sample drawn before the first treatment of the following week. Total bilirubin (not direct/conjugated) will be used for staging.

Other common etiologies for liver symptoms include drug toxicity, conditioning regimen toxicity, veno-occlusive disease, total parenteral nutrition, cholestasis, and infection.

Gut aGvHD Staging

Stool output will be reported as volumes for all inpatients and as episodes (frequency and consistency) for all outpatients. Patients weighing ≥ 50 kg will be graded using total stool volume per day (mL/day), while patients weighing < 50 kg will be evaluated for gut symptoms according to mL/kg/day, as a function of body weight.

For patients who weigh < 50 kg, every effort should be made to collect stool volumes as a daily average in milliliters over a 3-day period and must be completed before the first ECP treatment of the next treatment week. For diarrhea volumes, report liquid stool volume in the following order:

1. Average of 3 consecutive days, if available.
2. Otherwise, the 3 days closest to each other within 1 week.
3. Otherwise, the average of 2 consecutive days.
4. Otherwise, the maximum volume from the isolated day(s) available.

Formed or mostly formed stools should not be quantified or counted in the estimation of liquid stool volume. It will be noted on the source documents, if urinary mixing is present. For patients in diapers, the volume will be calculated from the weight of the diaper before and after use. For outpatients, Patient Stool Volume Records will be provided, according to usual site practice, along with instructions for collection and measurements. Stool volume collection should be done without regard to the ECP treatment schedule.

When diarrhea is reported as episodes instead of individual volumes, episodes of non-quantified liquid stool will be counted as 200 mL each for patients ≥ 50 kg and 4 mL/kg for patients < 50 kg.

When gross blood is present:

- Bloody diarrhea is staged as 4, even if low volume.
- Blood-streaked low volume (< 500 mL/day or < 10 mL/kg/day) stools (as can be seen with bleeding hemorrhoids, for example) are staged as 0.

For stage D or stage 4 gut involvement, severe pain is defined as:

- Pain that requires the start of narcotic use, or an increase in on-going narcotic use PLUS.
- Pain that significantly impacts performance status, as determined by the treating physician.

Other common etiologies for GI symptoms include drug toxicity, conditioning regimen toxicity, and infection.

Upper GI aGvHD Staging

The determination that nausea, vomiting and/or anorexia are persistent is based on clinical judgment. As a general rule, nausea lasting fewer than 3 days, fewer than 2 vomiting episodes per day for at least 2 days, and anorexia without weight loss should not be considered persistent.

Other common etiologies for upper GI symptoms include drug toxicity, conditioning regimen toxicity, infection, and total parenteral nutrition.

ECP Treatments

Patients should be scheduled to receive the first ECP treatment as soon as possible upon confirmation of eligibility. Patients must be enrolled and receive their first ECP treatment within 1 week (7 days) after being diagnosed as having steroid-refractory aGvHD. Week 1 (7 days) begins on the day the first ECP treatment is received (Day 1 of Week 1). The availability of typed and cross-matched donor PRBCs for transfusion during treatment, if needed, should be established prior to the scheduling of ECP treatments.

Prior to an ECP treatment, each patient will be assessed by a qualified health-care professional to verify that the patient is acceptable for ECP treatment. This assessment will include vital signs (diastolic and systolic blood pressures, pulse rate, respiratory rate and temperature) that will be taken before and at the end of each ECP treatment. Local laboratory analyses will be drawn before each ECP treatment, as specified above. If a patient's WBC count is $< 1.0 \times 10^9/L$ or platelet count is $< 20.0 \times 10^9/L$, that patient should NOT be treated with ECP until the WBC count is $\geq 1.0 \times 10^9/L$ and platelet count is $\geq 20.0 \times 10^9/L$ (platelet transfusions ARE permitted). This stipulation may require that patients receive one or more transfusions before the first or subsequent ECP treatments. Principal Investigators must use a coagulation-screening test of their choice in verifying a patient as acceptable for ECP treatment. The threshold value of the coagulation-screening test used to allow a patient to receive ECP treatment will be based upon a Principal Investigator's own clinical judgment. Patient monitoring during ECP treatment will be done according to institutional protocols in alignment with the CELLEX System Operator's Manual. Ionized calcium, if applicable, will be assessed before and during ECP treatments at the discretion of the Principal Investigator and according to institutional protocols.

For more information on ECP treatments, see the CELLEX System Operator's Manual.

Scheduling

The study coordinator will arrange the scheduling of ECP treatments according to the following schedule:

- Weeks 1-4: 3 treatments per week.
- Weeks 5-12: 2 treatments per week.

Patients are expected to receive the stated number of treatments per treatment week (7 days) \pm 2 days, and a total of no more than 12 ECP treatments for the first 28 days.

Extracorporeal photopheresis treatments given within ± 2 days of the expected treatment week will not be considered a protocol deviation.

Week 1 (7 days) begins when the first ECP treatment is received (Day 1 of Week 1). The availability of typed and cross-matched donor PRBCs for transfusion during treatment, if needed, should be established prior to the scheduling of ECP treatments.

After completion of the 12-week Treatment Period, patients may continue ECP treatment on commercial product at the discretion of the Principal Investigator.

Special Warnings and Precautions for Use

Patients should be explicitly instructed to wear UVA-absorbing, wrap-around sunglasses and cover exposed skin or use a sunblock (SPF 15 or higher) for the 24 hour period following treatment with methoxsalen, whether exposed to direct sunlight or indirect sunlight through a glass window.

Primary and Secondary aGvHD Endpoint Assessments (Weeks 4, 8, and 12)

Assessments of aGvHD status (including total bilirubin, corticosteroid dosing, Lansky Performance Status, etc.) for the purpose of the primary and secondary endpoint analyses should be performed at Days 28 (± 2), 56 (± 2) and 84 (± 2), respectively.

Concomitant Medications

All concomitant medications taken by patients during the Treatment Period, including those medications taken between visits, will be recorded on the Prior and Concomitant Medication Report Form of the eCRF. Concomitant medications should be recorded on a weekly basis.

Adverse Events

Patients will be asked about AEs that may have occurred after the patient signed and dated the ICF. Each patient will be asked about AEs using the non-specific question, "How have you been since your last visit?" Any AEs elicited by this question will be recorded on the Adverse Event Report Form of the eCRF, as well as any AEs spontaneously volunteered by the patient or observed by the study staff.

Nonrelapse Mortality

Nonrelapse mortality is defined as death due to any cause, with death due to relapse as a competing risk [Das-Gupta et al., 2014b].

Survival

Recipient Death Information must be entered into the eCRF within 24 hours of knowledge of a patient's death. Once the cause of death is determined, the information must be recorded in the eCRF.

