	
 • Weeks 1-4: 3 treatments per week. • Weeks 5-12: 2 treatments per week. 
Week 1 (7 days) begins when the first ECP treatment is received (Day 1 of Week 1). The availability of typed and cross-matched donor PRBCs for transfusion during treatment, if needed, should be established prior to the scheduling of ECP treatments.
 
Extracorporeal photopheresis treatments given within \pm 2 days of the expected treatment week will not be considered a protocol deviation.
 
Patients must be enrolled and receive their first ECP treatment within 1 week (7 days) after being diagnosed as having steroid-refractory aGvHD.
 
All patients will be evaluated for a response in their aGvHD manifestations at least once each week through Week 12, or the visit at which a patient ceases to receive treatment, if before Week 12. The assessment of aGvHD status should occur after the last ECP treatment of the week has been completed.
 
Principal Investigators should consult Appendix D: Fluid Balance Management and the CELLEX System Operator's Manual for information on minimum hematocrit and extracorporeal volume.
 
It is anticipated that most patients will receive ECP treatments in this protocol via a central venous catheter. However, Principal Investigators may choose to administer ECP treatments via peripheral venous access if clinically prudent.

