6.6 EARLY CESSATION OF STUDY PARTICIPATION

If the Principal Investigator, the Sponsor, or the Medical Monitor becomes aware of conditions that suggest a risk to safe participation in the study, study treatment will be discontinued. If the Principal Investigator, based on his/her medical judgment, determines there is a risk to the patient with continued participation in the study, the patient will be withdrawn. The study may also be terminated early for all patients at the Sponsor's discretion. Conditions that may warrant termination include, but are not limited to:

- The discovery of an unexpected, significant, or unacceptable risk to the patients enrolled in the study.
- Failure to enroll patients at an acceptable rate.
- A decision on the part of the Sponsor to suspend or discontinue development of the drug.
- Recommendation by the Data Safety Monitoring Board (DSMB).

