6.6.1 Early Cessation of Study Treatment

Patients *may* voluntarily stop receiving therapy at any time. The patient's legal guardian/legally authorized representative may choose to stop a patient's therapy at any time.

If a patient voluntarily ceases to receive therapy, the primary reason must be requested and, if provided, will be recorded on the Study Termination page of the eCRF.

The Principal Investigator and/or the Sponsor may also judge that early cessation of treatment is warranted for any one of the following reasons:

- Occurrence of AEs that pose a risk to safe participation.

- Abnormal laboratory value(s) that pose a risk to safe participation.
- Abnormal test procedure result(s) that pose a risk to safe participation.
- Unsatisfactory therapeutic effect.
- Condition no longer requires treatment.
- Significant protocol deviation.
- Patient non-compliance with protocol requirements.

Unless a patient/legal guardian/legally authorized representative withdraws study consent, patients will continue to be followed as per the trial protocol and clinical assessment schedule to ensure that full, intent-to-treat follow-up data are obtained.

For patients who are lost to follow-up, the Principal Investigator should show due diligence by documenting in the source documents steps taken to contact the patient (e.g., dates of telephone calls, emails).

Patients who voluntarily cease to receive treatment early will not be replaced. Patients will be replaced if they are enrolled in the trial but are not treated.

If a patient has received any ECP treatments and is administered a second-line therapy other than ECP for the treatment of aGvHD, or discontinues study treatment, that patient will be considered a nonresponder and may not be replaced.

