^b At a minimum, a bilirubin level should be checked before the first ECP treatment of each week to assist in assessing aGvHD status of the previous week. Platelets and total WBC count should be checked before each scheduled ECP treatment as clinically indicated to ensure that they meet pre-ECP safety parameters. Hematocrit should be checked according to the CELLEX System Operator’s Manual. Ionized calcium may be checked, at the discretion of the Principal Investigator. A new calculation of Total Blood Volume is necessary before each treatment to estimate the safe extracorporeal blood volume that may be allowed for the patient undergoing treatment. These calculations should be performed using the current weight (recorded at the first visit of the week) and current hematocrit (drawn after the last photopheresis treatment and within 48 hours before the next photopheresis treatment).

^c After the baseline aGvHD assessment at the beginning of Week 1, aGvHD assessments should be performed within the weekly treatment window (± 2 days) after the last ECP treatment of each treatment week.

^d A baseline aGvHD assessment, including blood sampling for total bilirubin should be performed before the first ECP treatment of Week 1.

^e The assessment of aGvHD for the primary endpoint must occur at Day 28 (± 2 days) and must include a total bilirubin level.

^f The assessment of aGvHD for the secondary endpoint must occur at Days 56 and 84 (± 2 days) and must include a total bilirubin level.

^g Patients should be told emphatically to wear UVA-absorbing, wrap-around sunglasses and to cover exposed skin or use a sunblock (SPF 15 or higher) for the 24 hour period following treatment with methoxsalen, whether exposed to direct or indirect sunlight in the open or through a glass window.

^h These laboratory assessments should be performed monthly, before the first ECP treatment of the week at Weeks 5 and 9:

- CBC with differential (WBC, platelets, hemoglobin, hematocrit, neutrophils, lymphocytes, basophils, eosinophils, and monocytes); absolute neutrophil count.
- Electrolyte panel (sodium, potassium, chloride, bicarbonate, BUN, creatinine, and glucose), BUN/creatinine ratio, calcium, phosphorous, and magnesium.
- AST, ALT, GGT, total bilirubin, direct bilirubin, indirect bilirubin, alkaline phosphatase, and lactate dehydrogenase.

ⁱ The assessment of aGvHD must be +/- 2 days of the endpoint assessments

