^j Early study termination applies to only to those patients who discontinue ECP prior to 12 weeks of treatment and do not remain on the study.

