7.2.4 Early Study Termination Visit

End of study assessments (Schedule of Assessments in [Table 1, Section 7.1](#)) will be completed for those patients who discontinue ECP, prior to completing 12 weeks of treatment, and will not remain in the study. The Early Study Termination page of the eCRF must be completed for these patients, with the reason for withdrawal from the study. For those patients who terminate early, every effort should be made to perform the early termination assessments.

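### Section 7.2.2 and the synopsis end weekly aGvHD staging when ECP stops, against section 6.6.1 and Table 1, so organ grades and the timing of response loss may go uncollected after the stop

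*Combined protocol and SAP*

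**What the plan says.** **The limiting rule.** Protocol section 7.2.2 (Assessment of aGvHD Status) has all patients evaluated "at least once each week through Week 12 (or the visit at which the patient ceases to receive treatment, if before Week 12". The synopsis, under dosage and frequency, carries the same limit: "or the visit at which a patient ceases to receive treatment, if before Week 12".

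**The continuing rule.** Section 6.6.1 provides that, unless consent is withdrawn, "patients will continue to be followed as per the trial protocol and clinical assessment schedule to ensure that full, intent-to-treat follow-up data are obtained".

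**Table 1.** The aGvHD status row is marked for every treatment week and for Week 16, with no condition that ECP is ongoing. Footnote e fixes the primary assessment at Day 28. Footnote f says "The assessment of aGvHD for the secondary endpoint must occur at Days 56 and 84". Both allow ±2 days and require a total bilirubin. Footnote j says that early study termination "applies to only to those patients who discontinue ECP prior to 12 weeks of treatment and do not remain on the study", so the plan foresees patients who stop ECP and stay in the study. A later paragraph of 7.2.2 repeats the Day 28, 56 and 84 endpoint assessments.

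**Endpoints and analysis.** Sections 3.2.2 and 9.3.2 time organ-specific grade at Days 28, 56 and 84 from the start of ECP, and run duration of response through Week 16, summarized by Kaplan-Meier. Sections 6.6.1 and 9.3.1 count a patient who discontinues study treatment as a nonresponder.

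**The concern.** The two rules give a site opposite instructions for the same patient. Someone who stops ECP at Week 5 and stays in the study needs no further weekly aGvHD evaluation under the 7.2.2 clause, but remains on the whole schedule under 6.6.1.

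Routine weekly staging is also described around ECP visits: clinical staging after the last treatment of the week, and bilirubin before the first treatment of the next. The weekly instructions therefore fit poorly once ECP has stopped, which makes the truncated reading easier to adopt.

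The nonresponder rule settles the CR+PR proportions without further staging. It does not supply an organ stage, and the documents do not say how stopping ECP enters the Kaplan-Meier analysis. Section 9.3 leaves analysis details to a formal analysis plan, but no analysis plan can recover stages that were never recorded. Section 3.4 ties the regulatory case to durable response, so the course of response after ECP stops is of interest.

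The reasons for stopping listed in 6.6.1 include both a poor treatment effect and a condition that has ceased to need treatment. The missing stages could therefore come from patients doing badly, patients doing well, or both.

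**Working it through.** The contradiction is textual, and the plan gives no figure on this point to reproduce. The first step compares the passages; the second shows how large the effect could be under stated assumptions.

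**Step 1. What each passage requires for a patient who stops ECP at Week 5 and does not withdraw consent**

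| Source | After the stop |
|---|---|
| 7.2.2 weekly evaluation clause; synopsis | No further weekly evaluation |
| 6.6.1 | Full assessment schedule continues |
| Table 1, aGvHD status row | Weekly through Week 12, then Week 16 |
| Table 1 footnote f; 7.2.2 endpoint paragraph | Days 56 and 84 (±2 days); footnote f requires total bilirubin |
| Table 1 footnote j; 7.2.4 | Early termination visit only if the patient also leaves the study |
| 3.1; 7.2.3; Table 1 | One aGvHD assessment at Week 16, not conditional on ECP |

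On the truncated reading, nothing is staged between the stop and Week 16. A responder found to have lost response at Week 16 could have lost it at any time in that gap.

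**Step 2a. Organ grade (illustration)**

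Inputs: N = 48 (section 9.1). Everything else is assumed: a share d of patients off ECP but in the study at Day 84, and proportions with organ improvement q_on (still on ECP) and q_off (stopped).

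- Patients graded on the truncated reading: 48 × (1 − d). For d = 0.1, 0.2, 0.3, 0.4 this is 43.2, 38.4, 33.6, 28.8, or about 43, 38, 34 and 29. About 5, 10, 14 and 19 are missing.
- Observed-case estimate minus all-treated value: q_on − [(1 − d) q_on + d q_off] = d × (q_on − q_off).
- q_on = 0.60, q_off = 0.40: 0.1 × 0.20 = 2 points, rising to 0.4 × 0.20 = 8 points.
- q_on = 0.60, q_off = 0.20: 0.1 × 0.40 = 4 points, rising to 0.4 × 0.40 = 16 points.
- If patients stop because they are well and the rates are swapped (q_on = 0.40 or 0.20, q_off = 0.60), the same sizes appear with a minus sign: −2 to −8 and −4 to −16 points.

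Using 48 as the denominator is a simplification, since not every patient has every organ involved.

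**Step 2b. Duration of response (illustration)**

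Assume a weekly hazard of losing response of 0.03 on ECP and h after stopping, and a weekly probability s of stopping, over the 8 weeks from Week 4 to Week 12.

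- Kaplan-Meier with censoring at the stop: (1 − 0.03)^8 = 78.4% still in response.
- All followed, by weekly recursion: on' = on × 0.97 × (1 − s); off' = off × (1 − h) + on × 0.97 × s.
- s = 0.02, 0.05, 0.08 means 1 − (1 − s)^8 = 15%, 34%, 49% stopping over 8 weeks.
- h = 0.03 (stopping uninformative): 78.4% in each case, difference 0.
- h = 0.10: 75.7%, 72.2%, 69.1%, so differences of 2.7, 6.2 and 9.3 points.
- If h were below 0.03, the sign would reverse.

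**The case against.** The strongest reply is that the plan already supplies the key visits. The endpoint paragraph in 7.2.2 and footnotes e and f fix Days 28, 56 and 84 by calendar. The opening of 7.2.2 sends the reader to Table 1 for timing, and stool collection is expressly independent of ECP. On this reading the clause limits only the routine weekly evaluations. The reading is reasonable and means the loss is not certain. It does not remove the conflict: 6.6.1 and Table 1 also keep the weekly evaluations, and no passage tells a site to prefer the narrower reading.

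Several stronger claims are tempting, but the documents do not support them.

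- A reader might infer that nothing prompts a visit once ECP stops, or that duration of response rests only on patients still on ECP. The calendar-fixed assessments answer the first. For the second, the Week 16 assessment does not depend on ECP, and patients contribute time up to their stop. The nonresponder rule in 6.6.1 could also be read as making a stop count as loss of response; the documents do not settle this.
- A reader might infer a bias in favour of ECP. With 60% of continuing patients and 10% of stoppers clear in an organ, (0.60 × (48 − k) + 0.10 × k)/48 gives 54.8%, 49.6% and 44.4% for k = 5, 10 and 15 stoppers, against 60% in observed cases: 5 to 16 points. The arithmetic is right, but the rates are invented, no passage specifies an observed-case summary, and stopping because treatment is no longer needed would push the other way.
- A reader might infer that the forms steer sites towards study exit, because 6.6.1 has the reason for voluntarily stopping therapy, which "will be recorded on the Study Termination page of the eCRF", while 7.2.4 says of patients leaving the study "The Early Study Termination page of the eCRF must be completed for these patients". The eCRF is not in the documents, and the 6.6.1 sentence covers voluntary cessation only, so this is inference.
- A reader might infer that section 6.6 contradicts 6.6.1 where an investigator "determines there is a risk to the patient with continued participation in the study, the patient will be withdrawn". Section 6.6 concerns study participation and 6.6.1 study treatment. What is unclear is only whether data follow-up continues for such patients.

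**Conclusion.** The contradiction is established from the text: 7.2.2 and the synopsis against 6.6.1, Table 1 with footnotes e, f and j, and the endpoint paragraph of 7.2.2 itself. It should be corrected, because a site can follow the protocol as written and still fail to collect data that 6.6.1 requires.

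The reach is limited. The primary endpoint and the other CR+PR proportions are protected by the nonresponder rule. What is exposed is organ-specific grade at Days 28, 56 and 84 for patients who have stopped by then, and the timing of response loss between the stop and the single Week 16 assessment.

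The size and direction of any bias cannot be derived, because no discontinuation rate is given and stopping may follow good or bad outcomes. The illustrative ranges (2 to 16 points either way for an organ-grade proportion; 0 to about 9 points for 8-week response when loss is no slower after stopping) depend wholly on the assumed rates and on sites adopting the truncated reading.

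**What to change.** - Delete the parenthetical clause on ceasing treatment from 7.2.2, and the matching words from the synopsis.
- Add to both: aGvHD staging, including total bilirubin, continues after ECP stops on the Table 1 schedule counted from the first ECP treatment, independent of any ECP visit, unless consent is withdrawn. This includes Days 28, 56 and 84 (±2 days) and Week 16. No new window at Week 16 is needed.
- Record the date and reason for stopping ECP for every patient who stops, separately from study exit.
- The sponsor should reconcile the withdrawal wording in 6.6 with 6.6.1 as regards data follow-up only. No withdrawal rule is proposed here.
- The analysis plan should then state how stopping ECP is handled for organ grade and in the Kaplan-Meier analysis.

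The cost is protocol wording and the separate recording of the ECP stop. The practical downside is some visits for patients who no longer attend for ECP, which 6.6.1 already requires.
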